4.0 TREATMENT PLAN

4.1 Administration of Study Drug

Ruxolitinib will be administered twice daily (bid), approximately 12 hours apart. The starting dose will be 20 mg bid for patients with a platelet count of $\geq 200 \times 10^9/L$ (dose level 1) and 15 mg bid for patients with a platelet count of $\geq 100 \times 10^9/L$ and $\leq 200 \times 10^9/L$ (dose level -1). The starting dose for patients a hemoglobin level of 12 -13 g/dL will be 10 mg bid (dose level -2). Dose adjustment (de-escalation) will be done in accordance with the scheme outlined in Table 4. Tablets will be taken without regard to food on an outpatient basis. Vomited doses can be made up, if the person vomits within 30 minutes after taking ruxolitinib. If the person vomits after 30 minutes upon taking ruxolitinib, the person may wait to take it when it is time to take the next dose.

Dose adjustments are required for protocol-specified clinically significant ruxolitinib-related adverse events (AEs) of Grade 3 or Grade 4 severity, declining platelet counts, declining absolute neutrophil counts (ANC) and declining hemoglobin levels (Table 4 and Section 5). Discontinuation of Ruxolitinib should be gradual to avoid "ruxolitinib withdrawal syndrome".

Table 4. Dose (mg) adjustment schema

b.i.d	Dose (b.i.d.)
1	20
-1	15
-2	10
-3	5

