2.1.1 Effect of Ruxolitinib in patients with CLL/SLL

Because no standard therapeutic intervention is available to control CLL/SLL patients' symptoms and because stimulation of the BCR activates the JAK/STAT3 pathway, known to induce the production of inflammatory cytokines (Rozovski et al., 2014), we conducted a clinical trial (protocol 2013-0044) to assess the effect of ruxolitinib on symptoms in CLL/SLL patients. After the enrollment of 40 patients onto this study we found that: **1.)** Ruxolitinib is well tolerated in patients with CLL/SLL. Very few patients had to be removed from the study because of adverse events. **2.)** The vast majority of the patients (78 %) responded to therapy, their symptoms improved, often dramatically, and the clinical improvement in the patients correlated with a significant reduction in plasma inflammatory cytokine levels. **3.)** In several patients, the number of peripheral blood lymphocyte counts increased and then decreased to or below baseline level, as observed in CLL/SLL patients treated with the Bruton tyrosine kinase (BTK) inhibitor Ibrutinib, suggesting that, like Ibrutinib, ruxolitinib induces mobilization and then apoptosis of CLL/SLL cells. Therefore we intend to explore whether ruxolitinib would reduce disease burden in patients with high-risk CLL/SLL.

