2.2.10 Warnings and precautions

Thrombocytopenia, Anemia and Neutropenia

Treatment with Jakafi can cause thrombocytopenia, anemia and neutropenia.. Manage thrombocytopenia by reducing the dose or temporarily interrupting Jakafi. Platelet transfusions may be necessary

Patients developing anemia may require blood transfusions and/or dose modifications of Jakafi. Severe neutropenia (ANC less than $0.5 \times 10^9/L$) was generally reversible by withholding Jakafi until recovery. Perform a pre-treatment complete blood count (CBC) and monitor CBCs every 2 to 4 weeks until doses are stabilized, and then as clinically indicated.

Risk of Infection

Serious bacterial, mycobacterial, fungal and viral infections have occurred. Delay starting therapy with Jakafi until active serious infections have resolved. Observe patients receiving Jakafi for signs and symptoms of infection and manage promptly.

Tuberculosis

Tuberculosis infection has been reported in patients receiving Jakafi. Observe patients receiving Jakafi for signs and symptoms of active tuberculosis and manage promptly. Prior to initiating Jakafi, patients should be evaluated for tuberculosis risk factors, and those at higher risk should be tested for latent infection. Risk factors include, but are not limited to, prior residence in or travel to countries with a high prevalence of tuberculosis, close contact with a person with active tuberculosis, and a history of active or latent tuberculosis where an adequate course of treatment cannot be confirmed.

For patients with evidence of active or latent tuberculosis, consult a physician with expertise in the treatment of tuberculosis before starting Jakafi. The decision to continue Jakafi during treatment of active tuberculosis should be based on the overall risk-benefit determination.

PML

Progressive multifocal leukoencephalopathy (PML) has occurred with ruxolitinib treatment for myelofibrosis. If PML is suspected, stop Jakafi and evaluate.

Herpes Zoster

Advise patients about early signs and symptoms of herpes zoster and to seek treatment as early as possible if suspected.

Hepatitis B

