Hepatitis B viral load (HBV-DNA titer) increases, with or without associated elevations in alanine aminotransferase and aspartate aminotransferase, have been reported in patients with chronic HBV infections taking Jakafi. The effect of Jakafi on viral replication in patients with chronic HBV infection is unknown. Patients with chronic HBV infection should be treated and monitored according to clinical guidelines.

Symptom exacerbation following interruption or discontinuation of treatment with Jakafi

Following discontinuation of Jakafi, symptoms from myeloproliferative neoplasms may return to pretreatment levels over a period of approximately one week. Some patients with myelofibrosis have experienced one or more of the following adverse events after discontinuing Jakafi: fever, respiratory distress, hypotension, DIC, or multi-organ failure. If one or more of these occur after discontinuation of, or while tapering the dose of Jakafi, evaluate for and treat any intercurrent illness and consider restarting or increasing the dose of Jakafi. Instruct patients not to interrupt or discontinue Jakafi therapy without consulting their physician. When discontinuing or interrupting therapy with Jakafi for reasons other than thrombocytopenia or neutropenia [see *Dosage and Administration (2.5)*], consider tapering the dose of Jakafi gradually rather than discontinuing abruptly.

Non-Melanoma Skin Cancer

Non-melanoma skin cancers including basal cell, squamous cell, and Merkel cell carcinoma have occurred in patients treated with Jakafi. Perform periodic skin examinations.

Lipid Elevations

Treatment with Jakafi has been associated with increases in lipid parameters including total cholesterol, low-density lipoprotein (LDL) cholesterol, and triglycerides. The effect of these lipid parameter elevations on cardiovascular morbidity and mortality has not been determined in patients treated with Jakafi. Assess lipid parameters approximately 8-12 weeks following initiation of Jakafi therapy. Monitor and treat according to clinical guidelines for the management of hyperlipidemia.

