2.2.13 Dosage and administration

The recommended starting dose of ruxolitinib is 15 mg given orally twice daily for MF patients with a platelet count between $100 \times 10^9/L$ and $200 \times 10^9/L$ and 20 mg twice daily for MF patients with a platelet count of $>200 \times 10^9/L$. There is limited information to recommend a starting dose for patients with platelet counts between $50 \times 10^9/L$ and $100 \times 10^9/L$. The maximum recommended starting dose in these patients is 5 mg twice daily and the patients should be titrated cautiously. Doses may be titrated based on safety and efficacy. Treatment should be interrupted for platelet counts less than $50 \times 10^9/L$ or ANC less than $0.5 \times 10^9/L$. After recovery of platelet and neutrophil counts above these levels, dosing may be restarted at 5 mg twice daily and gradually increased based on careful monitoring of blood cell counts.

Dose reductions should be considered if the platelet counts decreases below $100 \times 10^9/L$ with the goal of avoiding dose interruptions for thrombocytopenia. If efficacy is considered insufficient and platelet and neutrophil counts are adequate, doses may be increased by a maximum of 5 mg twice daily.

The starting dose should not be increased within the first four weeks of treatment and thereafter no more frequently than at 2-week intervals.

The maximum dose of ruxolitinib is 25 mg twice daily. If a dose is missed, the patient should not take an additional dose, but should take the next usual prescribed dose. Treatment may be continued as long as the benefit: risk remains positive.

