10.0 CRITERIA FOR REMOVAL FROM THE STUDY

Patients will be removed from the study for the following reasons:

1. Pattern of noncompliance.
2. Toxicity (grade 3 or 4) inducing clinical symptoms necessitating red blood cell or platelet transfusions and not alleviated after dose adjustment.
3. Disease progression that require another therapeutic intervention (an increase in peripheral blood lymphocyte count is expected. If needed anti-CD20 antibody treatment (Rituximab or Ofatumumab) or leukopheresis are allowed).
4. Lack of response (a reduction of 20% of tumor mass or PR) at 6 ± 2 months.
5. Unexpected events (medical or other) that would prevent the patient from staying on study.
6. Patient's or physician's choice. Compliance will be assessed by the P.I. based on the drug accountability documented by the site staff and monitored by the designee. The objective is 100% compliance and the P.I. and his staff will evaluate compliance at each visit, and take appropriate steps to optimize compliance. For the purpose of subgroup analyses, subjects with at least 80% compliance over the total duration of dosing from the first day of dosing to the analysis of the study will be considered to be compliant.

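### Section 4.1 tells investigators to taper ruxolitinib at every discontinuation, without the exceptions for suspected PML and for cytopenia that Section 2.2.10 provides

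*Combined protocol and SAP*

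**What the plan says.** Section 4.1 (Administration of Study Drug) requires dose adjustments for ruxolitinib-related grade 3 or 4 events and for "declining platelet counts, declining absolute neutrophil counts (ANC) and declining hemoglobin levels", pointing to Table 4 and Section 5. The next sentence reads "Discontinuation of Ruxolitinib should be gradual to avoid" a withdrawal syndrome. No reason for stopping is exempted.

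Section 2.2.10 (Warnings and precautions) treats the reasons for stopping differently. On PML it says "If PML is suspected, stop Jakafi and evaluate". On tapering, its advice is limited to one set of circumstances, "When discontinuing or interrupting therapy with Jakafi for reasons other than thrombocytopenia or neutropenia", and there the instruction is to "consider tapering the dose of Jakafi gradually rather than discontinuing abruptly".

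Two other places bear on how a stop comes about. Section 2.2.13 (Dosage and administration) contains a hold rule, "Treatment should be interrupted for platelet counts less than" 50 x 10^9/L, or for an absolute neutrophil count (ANC) below 0.5 x 10^9/L. Section 10.0 lists the reasons for removal, among them (item 2) grade 3 or 4 toxicity "inducing clinical symptoms necessitating red blood cell or platelet transfusions and not alleviated after dose adjustment", and (item 6) the patient's or physician's choice.

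**The concern.** Section 4.1 is where an investigator looks to find out how to give and stop the drug. Its sentence on stopping is broader than the safety text on which it appears to rest. Followed as written, it would have a patient with suspected PML continue at falling doses while the infection is being evaluated. It would also extend the taper to patients stopped for a low platelet or neutrophil count, a group that Section 2.2.10 leaves out of its taper advice. Nothing in the treatment section alerts the reader to either difference.

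What is at stake is the safety of individual patients and the clarity of an instruction. The statistical analysis is not involved.

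**Working it through.** The plan gives no figure on this point and no arithmetic applies. The check is a comparison of the texts.

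**1. Scope and strength.**

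| Reason for stopping | Section 4.1 | Section 2.2.10 |
|---|---|---|
| Suspected PML | Gradual | Stop and evaluate; no taper mentioned |
| Thrombocytopenia or neutropenia | Gradual | Outside the taper advice; a taper is neither advised nor forbidden |
| Any other reason | Gradual | Consider a taper |

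Section 4.1 is wider in scope in the first two rows. It is also firmer in tone: *should*, against *consider*.

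**2. Do the operative sections restore the exceptions?**
- Table 4 lists dose levels only.
- Section 5 covers interacting drugs, delays of up to one month, and renal and hepatic impairment. It does not say how to stop.
- Section 10.0 says when a patient comes off study, not how the drug is withdrawn.

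The sentence in Section 4.1 is therefore the only instruction in the treatment sections on how to discontinue.

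**3. Suspected PML.** The trigger is a clinical suspicion, so no blood-count threshold puts the drug on hold first. The two texts apply at the same moment and point in different directions. This part of the gap stays open.

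**4. Cytopenia.** Three features narrow the gap.
- Below the Section 2.2.13 thresholds (platelets 50 x 10^9/L, ANC 0.5 x 10^9/L) treatment is already interrupted, so nothing is left to taper.
- Above them, the protocol itself prescribes stepping the dose down as counts fall (Sections 4.1 and 2.2.13), which is close to a taper.
- Inclusion criterion 8 admits patients with an ANC as low as 0.5 x 10^9/L, and Section 4.1 sets the starting dose by platelets and hemoglobin. A reduced dose at an ANC just above 0.5 x 10^9/L is therefore not clearly outside what the protocol already accepts.

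What remains is a patient stopped for a low count while still on drug, for example for neutropenia by physician's choice.

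**5. Number affected.** The documents give no rate of permanent stops for these reasons in CLL. Section 2.1.1 reports of the preceding CLL trial: "Very few patients had to be removed from the study because of adverse events". The public description, which appears to concern that trial, gives its dose as 10 mg twice daily. Starting doses here are 20, 15 or 10 mg twice daily, so the experience may not carry over. For PML, the protocol mentions occurrence in myelofibrosis without a rate.

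**The case against.** The strongest reply is that the protocol, read as a whole, already deals with the matter. Section 2.2.10 states the exceptions, Section 2.2.13 gives hold thresholds, and a general *should* sits naturally beside specific instructions. An investigator may depart from it, and Section 10.0 allows removal at the physician's choice. For cytopenia this reply largely succeeds.

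It does not dispose of the PML case, where no hold intervenes. It also relies on readers going back to the background section. Local physicians may conduct alternate visits after month 8, and Section 8.1 lists what they receive: the consent, abstract, treatment schema and evaluation plan, but not the full protocol. The requirement that the center's physician approve dose changes limits this risk without removing the inconsistency.

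A second objection has force. Abrupt withdrawal carries its own hazard: Section 2.2.10 describes serious events, up to multi-organ failure, in some myelofibrosis patients after stopping. The documents do not show which risk is larger in CLL. The correction must therefore not push investigators towards abrupt stops for low counts.

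A reader might infer two stronger things. One is that Sections 4.1 and 2.2.10 contradict each other on cytopenia, so that such patients are forced to stay on drug. The texts do not support this: both are advisory, Section 2.2.10 exempts these stops without forbidding a taper, and Section 4.1 speaks of discontinuation, so temporary holds are untouched. The other is that Section 2.2.10 requires an abrupt stop for cytopenia. It does not say so.

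**Conclusion.** The point stands as a minor inconsistency in a drug-stopping instruction. Section 4.1 omits two exceptions that the protocol's own safety section contains. The omission matters chiefly for suspected PML and only slightly for cytopenia. The number of patients affected is probably small and cannot be estimated from the documents. No endpoint, power calculation or stopping rule depends on it.

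The conclusion rests on three assumptions:
- The instruction to stop for suspected PML means stopping without a taper. This is its natural sense, although the text does not use a word such as *abruptly*.
- The warnings in Section 2.2.10, which appear to be product-label text written for myeloproliferative neoplasms, are meant to apply to the CLL patients in this trial.
- The appendices, including the Investigators' Brochure, do not settle the matter. They were not available for this check.

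The trial is closed to entry, but Section 4.3 allows treatment for up to 3 years and longer after discussion, so the sentence can still govern any patient who remains on drug.

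**What to change.** Keep the sentence in Section 4.1 and add to its end: *except that the drug is stopped at once if PML is suspected, and a taper is not required when stopping for thrombocytopenia or neutropenia (see Section 2.2.10)*.

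The second half is deliberately permissive. It removes the expectation of a taper for cytopenia without making an abrupt stop the rule, and the taper advice stays in force for every other reason. The treatment schema sent to local physicians should carry the same clause if it repeats the Section 4.1 instruction.

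The cost is one clause, with no added visit, procedure or analysis.

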4.2 Treatment Compliance

Subjects will return all bottles of unopened, empty, and opened/partially used study drug at study visits. Investigative site staff will perform a count of returned pills to assess compliance, and this information will be reported on the Case Report Form (CRF). Study drug which is returned will be destroyed in accordance with the site's drug destruction policy. A standard institutionally approved diary may be issued to subjects.

4.3 Duration of Treatment and Subject Participation

Subjects will continue treatment as long as clinically indicated as judged by the Principal Investigator (PI) of the study or the attending physician for up to 3 years. Treatment beyond 3 years may be permitted after discussion with the PI. The discussion should be documented in the subject's medical record.

4.4 Patient Assessments

Patients will be presented with the informed consent at screening. They will fill out the Brief Fatigue Inventory (BFI) and the MD Anderson Symptom Inventory (MDSI) at each visit to MDA starting on Day 1. Patients will be seen at MDA during the screening period (-15-1 day), Day 1, Day 15 \pm 7 days, Month 2 \pm 7 days, Month 3 \pm 7 days, Month 6 \pm 2 months and Month 8 \pm 2 months, 10, 12, and so on. Every clinic visit to MDACC will include a routine physical examination, Brief Fatigue Inventory (BFI) and MD Anderson Symptom Inventory (MDSI) questionnaires and standard laboratory tests including CBC with differential and, plts, chemistries to include creatinine and ALT, Immunoglobulin levels (IgG, IgA and IgM), T cell counts and Beta-2 microglobulin (b2M).

If you can become pregnant, blood (about 1 teaspoon) and/or urine will be collected for a pregnancy test.

Correlative studies will be conducted to understand changes in the immunological and cytokine/chemokine pathways in CLL in response to ruxolitinib. Correlative studies will only be performed at MDACC visits: Day 1 (pre-dose), Month 3 \pm 7 days, and Month 6 \pm 2 mos. or as requested by the PI for specific patients with unusual response or unusual clinical presentation. Complete blood counts should be monitored every 2-4 weeks at MDACC or by the patient's local physician until counts are stabilized.

After month 8 \pm 2 mos the patient is required to have a physical exam, hematology and chemistry every 2 months \pm 2 mos. (Month 10, 12, and so on.) Every other visit may be conducted by the patient's local physician if more convenient for the patient.

Follow-Up

About 30 days after your last dose of ruxolitinib, blood (about 2 teaspoons) will be drawn for routine tests.

5.0 DOSING DELAYS/ DOSE MODIFICATIONS

5.1 Concomitant Use with Strong CYP3A4 Inhibitors or Fluconazole

Modify the dose of Jakafi when given concomitantly with strong CYP3A4 inhibitors (such as but not limited to boceprevir, clarithromycin, conivaptan, grapefruit juice, indinavir, itraconazole, ketoconazole, lopinavir/ritonavir, mibefradil, nefazodone, nelfinavir, posaconazole, ritonavir, saquinavir, telaprevir, telithromycin, voriconazole) and fluconazole doses of less than or equal to 200 mg as follows .

5.2 Dosing Delays

Up to a one month delay in the next dosing of Ruxolitinib, elected to be changed due to clinical side effects or laboratory abnormalities, is allowed.

5.3 Dose Modification of Ruxolitinib in Different Clinical Scenarios

Table 5. Dose modification for drug interactions

Patients on concomitant strong CYP3A4 inhibitors or fluconazole doses of less than or equal to 200 mg	Recommended Dose Modification
Starting Dose for Patients with Myelofibrosis with a platelet count:	

 • Greater than or equal to $100 \times 10^9/L$ 	10 mg twice daily

 • $50 \times 10^9/L$ to less than $100 \times 10^9/L$ 	5 mg once daily
Starting Dose for Patients with Polycythemia Vera	5 mg twice daily
All Patients on a Stable Dose of:	

 • Greater than or equal to 10 mg twice daily 	Decrease dose by 50% (round up to the closest available tablet strength)

 • 5 mg twice daily 	5 mg once daily

 • 5 mg once daily 	Avoid strong CYP3A4 inhibitor or fluconazole treatment or interrupt Jakafi treatment for the duration of strong CYP3A4 inhibitor or fluconazole use

Avoid the use of fluconazole doses of greater than 200 mg daily concomitantly with Jakafi. Additional dose modifications should be made with careful monitoring of safety and efficacy.

5.4 Renal Function Impairment

Modify the dose of Jakafi accordingly in patients with moderate or severe renal function impairment.

Table 6. Dosing for renal function impairment

Renal Impairment Status	Platelet Count	Recommended Starting Dosage
Patients with Myelofibrosis Moderate (CrCl 30–59 mL/min) or Severe (CrCl 15–29 mL/min)	Greater than $150 \times 10^9/L$	No dose modification needed
	$100 \times 10^9/L$ - $150 \times 10^9/L$	10 mg twice daily
	50 - less than $100 \times 10^9/L$	5 mg daily
	Less than $50 \times 10^9/L$	Avoid use [see Use in Specific Populations (8.6)]
Patients with Polycythemia Vera Moderate (CrCl 30-59 mL/min) or Severe (CrCl 15-29 mL/min)	Any	5 mg twice daily

5.4.1 Patients on dialysis

The recommended starting dose for patients with myelofibrosis with end stage renal disease on dialysis is 15 mg once after a dialysis session for patients with a platelet count between $100 \times 10^9/L$ and $200 \times 10^9/L$ or 20 mg for patients with a platelet count of greater than $200 \times 10^9/L$. The recommended starting dose for patients with polycythemia Vera with end stage renal disease on dialysis is 10 mg. Additional dose modifications should be made with frequent monitoring of safety and efficacy. Avoid use of Jakafi in patients with end stage renal disease (CrCl less than 15 mL/min) not requiring dialysis.

5.5 Hepatic Impairment

The dose of Jakafi should be reduced in patients with hepatic impairment.

Table 7. Dosing for hepatic impairment

Hepatic Impairment Status	Platelet Count	Recommended Starting Dosage
---------------------------	----------------	-----------------------------

Patients with Myelofibrosis Mild, Moderate, or Severe (Child- Pugh categories A, B, C)	Greater than $150 \times 10^9/L$	No dose modification needed
	$100 \times 10^9/L$ - $150 \times 10^9/L$	10 mg twice daily
	50 - less than $100 \times 10^9/L$	5 mg daily
	Less than $50 \times 10^9/L$	Avoid use [see Use in Specific Populations (8.6)]
Patients with Polycythemia Vera Mild, Moderate, or Severe (Child- Pugh categories A, B, C)	Any	5 mg twice daily

